The use of cold-water immersion has become a popular post-exercise recovery strategy despite a lack of evidence of its efficacy. Indeed, much of the data available of the human skeletal muscle response to local cold has used a cold-water immersion protocol. Strength training adaptations appear to be blunted when incorporating cold water immersion (36), which may be due to suppressed ribosome biogenesis (37) and anabolic signaling (38). Low cell culture temperature inhibits myogenic differentiation (39), and anabolic response (10, 40). These results are not without controversy as other applied studies and subsequent meta-analysis have shown a mild benefit of cold interventions (41). The current studies will help understand the disconnect between applied human model studies and mechanistic studies in rodents and cell culture by implementing molecular cell-signaling data into our human model.

Investigator's previous work and the foundational studies presented above will allow us to take a strategic approach and build off the previous work. We will take applied study design cues from the previous human studies and incorporate mechanistic components from rodent and culture studies. Furthermore, the studies proposed here will be able to determine the potential separate effects of temperature and those of effects of temperature only observable in the presence of exercise.

Participants

12 participants, age 19 to 45, will need to complete the study in order to achieve the scientific objectives of the research. Keeping an age range of 19-45 ensures that the participants will be relatively homogenous in terms of overall health and thus not present added risk.

Research Plan

A total of 2 visits to the laboratory will be required following the signing of informed consent. Given participant consent, photographs may be taken during the trials to document the research and use in future presentations.

Initial Visit (~1.5-2 hours):

Participants will complete a risk stratification form based on ACSM guidelines and must be considered low risk in order to participate in this study. Height and weight will be measured using a medical scale. Body fat will be assessed with hydrostatic weighing using an electronic load cell-based system (Exertech, Dresbach, MN) correcting for residual lung volume, or BIA body composition analyzer (InBodyUSA, Cerritos, CA) if needed.

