A total of 6 muscle biopsies (1 per leg) will be obtained from the vastus lateralis (outer thigh) muscle. One from each leg for each of the three collection time-points, pre-exercise, immediately post-exercise, and post-4-hour recovery. The PI will conduct these biopsies, having successfully completed over 600 biopsies without any adverse events. Briefly, the area above the vastus lateralis muscle belly will be shaved and cleaned with alcohol. 1% xylocaine is then injected under the skin with a 25 ga hypodermic needle. The Xylocaine will be ordered with a prescription provided by the participating physician.

The area is then further disinfected with betadine, and a sterile fenestrated drape is placed over the biopsy site. Using sterile techniques, a small incision is made through the skin (~5mm) and the Bergstrom biopsy needle is inserted through the incision into the belly of the muscle. The Bergstrom needle then takes a small clip of muscle (~50mg) and is removed from the muscle and stored in a chemical stabilizer at -30°C. Slight pressure is held over the incision for approximately 2 minutes and is then closed using steri-strips and a band-aid with antibiotic ointment. The leg is further dressed with a compression bandage.

Participants are all instructed how to care for the wound and given the investigators contact information in case they have further questions.

Intramuscular Temperature

Using the incision from the muscle biopsy, a hypodermic (~26ga) thermocouple (Physitemp Instruments LLC, Clifton, NJ) that is smaller than the needle used to inject the xylocaine will be inserted into the belly of the muscle to measure intramuscular temperature. The thermocouple readings stabilize in approximately 3 seconds and the thermocouple is then removed. Under normal circumstances, the sensation of this temperature reading is similar to an intramuscular injection. However, with the use of the biopsy incision as the insertion point there is very little sensation associated with this measure. Recordings for intramuscular temperature will be collected during the biopsy process following the 4-hour temperature intervention.

Skin Temperature

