Skin Temperature will be measured on the surface of each thigh using a skin thermistor (Physitemp Instruments LLC, Clifton, NJ), infrared digital thermometer, and/or using an infrared thermal camera. Measurements will be taken at the same time as the intramuscular. The thermistor is simply placed on the skin for approximately 3 seconds and is then recorded. The infrared digital thermometer can measure and record surface temperature from a distance of 12 inches. The infrared thermal camera can measure and record surface temperatures for a field of multiple surfaces.

Gene Expression Analysis

The muscle tissue collected will be processed and analyzed for transcriptional changes of genes associated with muscle growth and breakdown. Muscle mRNA content will be evaluated using real-time reverse transcription quantitative polymerase chain reaction (real- time RT-qPCR). Quantification of mRNA for genes of interest will be computed using the $2-\Delta\Delta CT$ method and compared to stable reference genes. Probes and Primers that will target the specific gene sequences will be attained from Integrated DNA Technologies (IDT, Coralville, IA).

Protein Expression Analysis

The muscle tissue collected will be processed and analyzed for proteins associated with muscle growth and breakdown. Standard western blotting protocols will be optimized and used to evaluate the muscle growth signaling cascade, using antibodies specific to the proteins of interest and normalized to total protein.

Statistical Analysis

Recruitment

Previous exercise research suggests that the difference in response of matched pairs is normally distributed with a standard deviation of 0.86. If the true difference of the mean response of matched pairs is 0.75, we will need to complete 12 experimental trials for each condition to be able to reject the null hypothesis that this response difference is zero with a power of 0.8. The Type I error probability associated with this test of the null hypothesis is 0.05.

Interventions

A repeated measures two-way ANOVA will be used for the dependent variables. If the F-ratio values are found to be significant then a Fishers protected Least Significant Difference post hoc will be performed to evaluate where the significance occurs. The probability of type I error must be less than 5% in order to be considered significant ($p < 0.05$). All Statistical data will be analyzed using the Statistical Package for Social Sciences software (SPSS 24.0)

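### The repeated measures ANOVA, in its standard form, drops a participant's five valid values when one of six samples fails for a marker; a mixed model would keep them, a conditional gain in precision

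*Combined protocol and SAP*

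**What the plan says.** The combined protocol and SAP, under Statistical Analysis (Interventions), gives one method for all outcomes: "A repeated measures two-way ANOVA will be used for the dependent variables". It is to be run in SPSS 24.0, with no procedure within that package named.

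The Biopsies section sets six samples per participant: "One from each leg for each of the three collection time-points". Each is a clip of about 50 mg, and the collected tissue serves both the RT-qPCR and the western blot work.

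The Participants section states that "12 participants, age 19 to 45, will need to complete the study in order to achieve the scientific objectives of the research". Under Statistical Analysis (Recruitment), the size is justified for one matched-pair comparison: "the difference in response of matched pairs is normally distributed with a standard deviation of 0.86", a true difference of 0.75, type I error 0.05, and the conclusion that "we will need to complete 12 experimental trials for each condition" to reach power 0.8.

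The documents contain no rule for a failed, inadequate or missing sample, no repeat-assay rule, no allowance for sample loss, and no model that would use an incomplete participant.

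**The concern.** A leg-by-time ANOVA with both factors within the person works, in its standard form, on complete rows of six cells. If one biopsy yields too little tissue, or one RNA extraction or blot lane fails, the participant leaves the analysis of that marker together with five good values.

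The count of 12 refers to people who complete the study. It is not tied to six usable results for each gene and protein, so it does not clearly protect against assay failure. Deletion would also work marker by marker, so markers in the same pathway could be tested on different subsets of participants.

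At stake is precision. With 12 people each one counts, and the tissue being set aside was obtained invasively.

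**Working it through.** **Inputs.** From Statistical Analysis (Recruitment): paired difference 0.75, SD of the difference 0.86, alpha 0.05, 12 pairs, power 0.8. Sidedness is not stated, so two-sided is assumed. From Biopsies: 2 legs × 3 times = 6 samples per participant, 12 × 6 = 72 in all. The failure rate q per sample is not in the documents; 1%, 2%, 5% and 10% are assumed, with failures independent.

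**1. The plan's own figure.** Standardised difference = 0.75/0.86 = 0.872. With n pairs, the paired t statistic is noncentral t with n − 1 degrees of freedom and noncentrality 0.872 × √n. At n = 12 the noncentrality is 3.02, the critical value is 2.201 and power is 0.785. The smallest n reaching 0.80 is 13 (0.823). The stated 12 therefore reproduces closely, but with no reserve.

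**2. Cost of each participant lost.**

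| Complete participants | 12 | 11 | 10 | 9 | 8 |
|---|---|---|---|---|---|
| Power | 0.785 | 0.741 | 0.690 | 0.632 | 0.565 |

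Three failed samples in three different people (3/72 = 4.2%) leave 9 participants and power 0.632. If three of the 72 are lost at random, the expected number complete is 12 × C(66,3)/C(72,3) = 9.2, with simulated power about 0.65.

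**3. Range over assumed failure rates.** The chance that a participant is usable is
- (1 − q)^6 if all six samples are needed (complete case);
- (1 − q)^4 if a leg difference in change from pre-exercise is tested on available data (both legs, two times);
- (1 − q)^2 if a leg difference at one time is tested on available data (both legs, one time).

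Power is the step 1 formula averaged over Binomial(12, that chance).

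| q | (1 − q)^6 | Mean complete of 12 | Power, six needed | Power, four needed | Power, two needed |
|---|---|---|---|---|---|
| 1% | 0.94 | 11.3 | 0.75 | 0.76 | 0.77 |
| 2% | 0.89 | 10.6 | 0.72 | 0.74 | 0.76 |
| 5% | 0.74 | 8.8 | 0.61 | 0.67 | 0.73 |
| 10% | 0.53 | 6.4 | 0.43 | 0.55 | 0.67 |

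The chance that all 12 are complete for a given marker is (1 − q)^72: 23% at 2% and 2.5% at 5%.

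**4. What deletion itself costs.** The fair baseline is 0.785, not 0.80. At 2% the complete-case drop is 0.785 − 0.72 = about 0.07, of which available data recover 0.02 (four samples) to 0.04 (two samples). At 5% the drop is 0.785 − 0.61 = about 0.17, of which they recover 0.06 to 0.12.

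These figures use the plan's paired-difference power statement. They are not the power of the ANOVA interaction test or of the mixed model proposed below, which were not computed.

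**The case against.** **Listwise deletion is not stated.** This is true. The plan names SPSS 24.0 without a procedure, and that package can also fit mixed models. But the method named is a repeated measures ANOVA, whose standard form needs all six cells, and no alternative is given. The inference is reasonable and remains an inference.

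**The failure rate is assumed.** This also stands. At 1% the loss is about three points. Independent failure is the harsher pattern: several failures in one person cost only that person, and a single lost sample still leaves 11 participants and 0.741. The statement in Biopsies about more than 600 procedures concerns adverse events, not tissue yield or assay success, so it does not settle the rate either way.

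**The 12 may already mean 12 with usable data.** The wording permits that, but completion is not defined by usable samples for each marker, and no replacement rule is given.

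**The two-sample comparison flatters the remedy.** This is fair where the response is a change from pre-exercise, which the documents do not say. The four-sample figures are therefore shown beside it, and the gain is then about half as large.

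**Bias.** A reader might infer that the contrast is biased if failures are commoner in the cooled leg or at a later time. That does not follow. If failure depends only on leg or time, participants with all six values are still a random subset and the within-person contrast is unbiased. Bias needs failure to depend on the participant or on the marker value.

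**Conclusion.** The point stands as a conditional gain in precision. Following the plan as written, one failed sample would remove a participant's other valid values for that marker, and the design has no reserve to absorb this. The cost in power, against a baseline of 0.785, is about 3 points at 1% failure, 7 at 2%, 17 at 5% and 35 at 10%. Available data would recover part of it: 1 to 2, 2 to 4, 6 to 12 and 11 to 23 points respectively, depending on whether four or two samples are needed.

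This rests on a two-sided paired test, independent failures at an assumed rate, and the standard complete-case form of the ANOVA. A reader might conclude that the trial will fall well short of its stated power. The documents do not support that: they give no failure rate, and the shortfall becomes material only once two or three participants are affected. Nor should the whole gap to 0.80 be put down to lost samples, since 12 complete pairs already give slightly less.

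**What to change.** In Statistical Analysis (Interventions), replace the repeated measures ANOVA, for both gene and protein markers, with a linear mixed model fitted to all available samples:
- fixed effects of leg, time and leg × time;
- random effects of participant, participant-by-leg and participant-by-time;
- Satterthwaite degrees of freedom;
- a named simpler random structure to use if a variance component is estimated at zero.

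Report, for each marker, the number of usable leg pairs at each time.

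**Cost.** SAP wording only: no extra participants or biopsies, and SPSS already fits such models. A covariance structure and its fallback must be named in advance. With 12 participants and one value per cell, a variance component may well be estimated at zero, and the F-tests can then differ slightly from the ANOVA even with complete data; otherwise, with complete balanced data, they are essentially the same.

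**Limit.** If the pre-exercise sample is the calibrator for the 2-ΔΔCT calculation (the plan does not say), losing it also removes that leg's later values, and no mixed model restores them.
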